5.2.2 Timing of Dose Administration

Trial treatment should be administered after all procedures/assessments have been completed as detailed in the Study Flow Charts (Section 6.0). Trial treatment may be administered [REDACTED]

[REDACTED] due to administrative reasons but only after consultation with the sponsor. All trial treatments will be administered on an outpatient basis. The Procedures Manual contains specific instructions for dose calculation, reconstitution, preparation of the infusion fluid, and administration.

5.2.2.1 Combination Dosing (Part A & Part B)

For Combination dosing, MEDI4736 will be given Q2W (Weeks 1, 3, 5, and 7 of each 8-week cycle) and ADXS11-001 will be given Q4W (Weeks 1 and 5 of each 8-week cycle). On days when both treatments are administered (Weeks 1 and 5 of each cycle), subjects will first receive the MEDI4736 infusion in 250 mL [REDACTED]

[REDACTED] after end of MEDI4736 infusion, subjects should be premedicated with NSAIDS and oral antiemetics (Section 7.1.4.2). **The ADXS11-001 infusion can begin [REDACTED] after the subject has been premedicated.** When given the same day as MEDI4736, ADXS11-001 will be given *in 100 mL* of normal saline [REDACTED], to reduce the potential for fluid overload.

Any subject administered ADXS11-001 will also receive antibiotics. Specific details of antibiotic regimen are provided in Section 7.1.4.2.

5.2.2.2 ADXS11-001 Monotherapy (Part B)

In Part B, the dose for ADXS11-001 monotherapy will be 1×10^9 cfu administered in 250 mL of normal saline infused [REDACTED] Q4W (Weeks 1 and 5 in each 8-week cycle). Subjects should be premedicated with NSAIDS and oral antiemetics and received antibiotic as indicated in Section 7.1.4.2.

5.2.2.3 MEDI4736 Monotherapy (Part B)

In Part B, the dose for MEDI4736 monotherapy will be 10 mg/kg administered in 250 mL of normal saline infused [REDACTED] in duration Q2W (Weeks 1, 3, 5, and 7 in each 8-week cycle).

5.2.3 Trial Blinding/Masking

This is an open-label trial; therefore, the sponsor, investigator and subject will know the treatment administered.

5.3 Randomization or Treatment Allocation

All subjects in Part A will receive combination therapy. Subjects participating in Part B will be allocated by random assignment 1:1:2 to ADXS11-001 monotherapy, MEDI4736 monotherapy, or ADXS11-001+ MEDI4736 combination therapy.

5.4 Stratification

In Part B, all 3 treatment arms will be stratified by disease (SCCHN or cervical cancer).

5.5 Concomitant Medications/Vaccinations (allowed & prohibited)

Medications or vaccinations specifically prohibited in the exclusion criteria are not allowed during the ongoing trial. If there is a clinical indication for one of these or other medications or vaccinations specifically prohibited during the trial, discontinuation from trial therapy or vaccination may be required. The investigator should discuss any questions regarding this with the Sponsor. The final decision on any supportive therapy or vaccination rests with the investigator and/or the subject's primary physician. However, the decision to continue the subject on trial therapy or vaccination schedule requires the mutual agreement of the Investigator, the Sponsor, and the subject.

5.5.1 Acceptable Concomitant Medications

All treatments that the investigator considers necessary for a subject's welfare may be administered at the discretion of the investigator in keeping with the community standards of

medical care. All concomitant medication will be recorded on the case report form (CRF) including all prescription, over-the-counter (OTC), herbal supplements, and IV medications and fluids. If changes occur during the trial period, documentation of drug dosage, frequency, route, and date may also be included on the CRF.

All concomitant medications received within 28 days before the first dose of trial treatment and 30 days after the last dose of trial treatment should be recorded. Concomitant medications, administered after 30 days after the last dose of trial treatment, for SAEs and ECIs should be recorded as defined in Section [7.2](#).

5.5.2 Prohibited Concomitant Medications

Subjects are prohibited from receiving the following therapies during the Screening and Treatment Phase (including retreatment for post-complete response relapse) of this trial:

- Anti-cancer therapy including but not limited to, hormonal, chemotherapy, radiation therapy, treatment with targeting agents (e.g. Tyrosine kinase inhibitors). However occasional radiation therapy for palliation of pain is allowed
 - Note: Radiation therapy to a symptomatic solitary lesion or to the brain may be allowed after consultation with Sponsor. Radio-pharmaceuticals (e.g., radium, strontium, etc.) are not acceptable.
- Immunotherapy not specified in this protocol
- Investigational agents other than ADXS11-001 and MEDI4736
- Live vaccines (e.g., measles, mumps, rubella, chicken pox, yellow fever, rabies, BCG, typhoid and intranasal influenza vaccines (e.g. Flu-Mist®). Seasonal influenza vaccines for injection are generally killed virus vaccines and are allowed.
- Chronic use of systemic glucocorticoids have the potential to reduce the immune response therefore should be used with caution. However, glucocorticoids should

be considered to manage symptoms of cytokine release (e.g. Fever, headache, hypotension, chills, rigors, etc.). Topical use of steroids is allowed. The occasional use of steroids for the treatment of COPD and or asthma is allowed.

- Anti-infectives should be avoided, except where mandated by the protocol. However, subjects with a documented infectious complication should receive oral or IV antibiotics or other anti-infective agents as considered appropriate by the treating investigator for a given infectious condition, according to standard institutional practice.
- Acetaminophen should not be substituted for the selected NSAID for pretreatment prophylaxis since acetaminophen does not have similar anti-inflammatory properties that could ameliorate cytokine release syndrome symptoms. Acetaminophen can be used after dosing for supportive care measures.

Subjects who, in the assessment by the investigator, require the use of any of the aforementioned treatments for clinical management should be removed from the trial. Subjects may receive other medications that the investigator deems to be medically necessary.

The Exclusion Criteria describe other medications which are prohibited in this trial.

There are no prohibited therapies during the Post-Treatment Follow-up Phase.

5.6 Supportive Care Guidelines

Subjects should receive appropriate supportive care measures as deemed necessary by the treating investigator including but not limited to the items outlined below.

5.6.1 Cytokine Release Syndrome

CRS per CTCAE V4.03 is characterized clinically by nausea, headache, tachycardia, hypotension, rash and shortness of breath. These side effects can develop soon after the administration of the *Lm*-LLO immunotherapies and can last for several hours. The clinical

syndrome is caused by a sudden increase in TNF α , IFN γ and IL-6 release, all of which have been shown to occur after *Lm*-LLO immunotherapy administration, resulting from the body's immune response to the therapy.

- Symptoms associated with CRS have been seen in subjects with ADXS11-001 administration. Symptoms are often grade 1-2 and transient, resolving with symptomatic management within 30 minutes-1 hour. In rare instance <5%, grade 3 rigors and hypotension have been seen.
- Prophylaxis with NSAIDs and anti-emetics have been shown to reduce both the severity, time to resolution and incidence. Supportive measure which include fluids for hypotension and continued use of NSAIDs are recommended.
- In cases of grade 3 hypotension that are not responsive to IV fluids consider use of low dose systemic corticosteroids (e.g. 100 mg, IV hydrocortisone infused over 30 seconds every 2 hours until resolution to Grade 1 or baseline or 500 mg IV hydrocortisone infused over 10 minutes every 2 hours until resolution to Grade 1 or baseline).

For subjects who experience symptoms associated with CRS, refer to [Table 3](#) for treatment modifications for subsequent infusions

5.6.2 Diarrhea

Subjects should be carefully monitored for signs and symptoms of enterocolitis (such as diarrhea, abdominal pain, blood or mucus in stool, with or without fever) and of bowel perforation (such as peritoneal signs and ileus). In symptomatic subjects, infectious etiologies should be ruled out, and if symptoms are persistent and/or severe, endoscopic evaluation should be considered.

- All subjects who experience diarrhea should be advised to drink liberal quantities of clear fluids. If sufficient oral fluid intake is not feasible, fluid and electrolytes should be substituted via IV infusion.

5.6.3 Nausea/vomiting:

Nausea and vomiting should be treated aggressively. Consideration should be given in subsequent cycles to the administration of prophylactic antiemetic therapy according to standard institutional practice. Subjects should be strongly encouraged to maintain liberal oral fluid intake.

5.6.4 Management of Infusion Reactions

With any infusional therapy there is the possibility of an infusion reaction. Signs and symptoms usually develop **during or shortly after drug infusion and generally resolve completely within 24 hours of completion of infusion**. Signs/symptoms may include: allergic reaction/hypersensitivity (including drug fever); arthralgia (joint pain); bronchospasm; cough; dizziness; dyspnea (shortness of breath); fatigue (asthenia, lethargy, malaise); headache; hypertension; hypotension; myalgia (muscle pain); nausea; pruritus/itching; rash/desquamation; rigors/chills; sweating (diaphoresis); tachycardia; tumor pain (onset or exacerbation of tumor pain due to treatment); urticaria (hives, welts, wheals); vomiting. See [Table 5](#) for treatment guidelines for subjects who experience an infusion reaction.

Table 5 Treatment Guidelines for Infusion Reactions

NCI CTCAE Grade	Treatment
Grade 1 Mild reaction; infusion interruption not indicated; intervention not indicated	Increase monitoring of vital signs as medically indicated until the subject is deemed medically stable in the opinion of the investigator.
Grade 2 Requires infusion interruption but responds promptly to symptomatic treatment (e.g., antihistamines, NSAIDS, narcotics, IV fluids); prophylactic medications indicated for ≤ 24 hrs.	
 1. Stop Infusion and monitor symptoms. 2. Additional appropriate medical therapy may include but is not limited to: 
IV fluids Antihistamines NSAIDS Acetaminophen Narcotics
 3. Increase monitoring of vital signs as medically indicated until the subject is deemed medically stable in the opinion of the investigator. If symptoms resolve within one hour of stopping drug infusion, the infusion may be restarted at 50% of the original infusion rate (e.g. from 100 mL/hr. to 50 mL/hr.). Otherwise dosing will be held until symptoms resolve and the subject should be premedicated for the next scheduled dose.
Grades 3 or 4 Grade 3: Prolonged (i.e., not rapidly responsive to symptomatic medication and/or brief interruption of infusion); recurrence of symptoms following initial improvement; hospitalization indicated for other clinical sequelae (e.g., renal impairment, pulmonary infiltrates) Grade 4: Life-threatening; pressor or ventilatory support indicated	
 1. Stop Infusion. 2. Additional appropriate medical therapy may include but is not limited to: 
IV fluids Antihistamines NSAIDS Acetaminophen Narcotics Oxygen Pressors Corticosteroids Epinephrine
 3. Increase monitoring of vital signs as medically indicated until the subject is deemed medically stable in the opinion of the investigator. 4. Hospitalization may be indicated. 5. Subject experiencing Grade 4 reactions will be permanently discontinued from further trial treatment administration. Subjects with Grade 3 reactions may continue after discussion with the sponsor.

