5.2.1.3 Treatment Modification

In Part A, dose escalation/de-escalation for MEDI4736 in the combination will be based on defined DLT criteria (Section 5.2.1.1); the ADXS11-001 combination therapy dose is 1×10^9 cfu (fixed). In the event of DLT, the investigator will determine relatedness to the study treatment combination.

With ADXS11-001 treatment, a clear pattern of treatment-related AEs consistent with cytokine release has emerged consisting of transient Grade 1 or 2 (mild-moderate) flu-like or cytokine release syndrome symptoms (such as chills, nausea and vomiting), the majority of which occur within the first 6 hours after infusion (see also Section 5.6.1). Symptoms either self-resolve or respond quickly to symptomatic treatment. There has been no evidence of listeriosis, no persistent symptoms, no delayed symptoms, and no evidence of cumulative

toxicity in subsequent doses. Treatment modification guidelines for cytokine release syndrome symptoms are shown in [Table 3](#). Treatment modification guidelines for irAEs are shown in [Table 4](#) below.

Table 3 Treatment Modification Guidelines for ADXS11-001 Cytokine Release Syndrome symptoms

Toxicity	Grade	Modification
1st episode of symptoms associated with CRS (e.g. Nausea, vomiting, chills, rigors, hypotension, fever)	1-2	No modification on subsequent ADXS11-001 infusion
	3-4	
Extend infusion time [REDACTED][REDACTED]Consider increasing prophylaxis dose of NSAIDSConsider incorporating pretreatment fluids to manage hypotension.
Second episode of CRS	1-2	No modifications
	3	Discussion with sponsor required
	4	If symptoms have not ameliorated from aforementioned modifications, subject should be discontinued from study

Table 4 Dose Modification Guidelines for Immune-related Adverse Events - MEDI4736 Monotherapy and Combination Arms

Severity	Immune-related Adverse Events (irAEs) ^a	All Other Events
Grade 1	None	None

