Grade 3	
For endocrinopathy: Hold MEDI4736/Combination dose. When endocrinopathy is controlled, resume MEDI4736/Combination administration at next scheduled dose.
 
For dermatologic irAEs: Hold MEDI4736/Combination until resolution to \leqGrade 1 or baseline. If resolution to \leqGrade 1 or baseline does not occur within 30 days, discontinue MEDI4736/Combination.
 
For elevations in transaminases: For elevations in transaminases up to $8 \times$ ULN, hold MEDI4736/Combination until resolution to \leqGrade 1 or baseline. If elevations downgrade to \leqGrade 2 within 7 days or resolve to \leqGrade 1 or baseline within 14 days of onset, resume MEDI4736/Combination administration at next scheduled dose. Otherwise, discontinue MEDI4736/Combination. For elevations in transaminases $>8 \times$ ULN, discontinue MEDI4736/Combination.
 
For elevations in bilirubin: For elevations in bilirubin up to $5 \times$ ULN, hold MEDI4736/Combination until resolution to \leq Grade 1 or baseline. If elevations downgrade to \leq Grade 2 ($< 3 \times$ ULN) within 7 days or resolve to \leq Grade 1 or baseline within 14 days, resume MEDI4736/Combination administration at next scheduled dose. Otherwise, discontinue MEDI4736.
 
For all other irAEs: Discontinue MEDI4736/Combination.
	
Hold MEDI4736/Combination until resolution to \leqGrade 1 or baseline. For AEs that downgrade to \leqGrade 2 within 7 days or resolve to \leqGrade 1 or baseline within 14 days, resume MEDI4736/Combination administration at next scheduled dose. Otherwise, discontinue MEDI4736/Combination.

Grade 4	Discontinue MEDI4736/Combination.	Discontinue MEDI4736/Combination.

AE = adverse event; irAE = immune-related adverse event; ULN = upper limit of normal.

^a Management of irAEs may require administration of immunosuppressive medications (and/or hormone replacement therapy for endocrinopathies). Resolution of irAEs managed in this manner in the timeframes specified is acceptable.

^b Subjects who require corticosteroids for resolution must have discontinued corticosteroids. Subject can restart study therapy upon resolution of irAE and cessation of corticosteroid treatment for 14 days.

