5.8 Subject Withdrawal/Discontinuation Criteria

Subjects may withdraw consent at any time for any reason or be dropped from the trial at the discretion of the investigator should any untoward effect occur. In addition, a subject may be withdrawn by the investigator or the Sponsor if enrollment into the trial is inappropriate, the trial plan is violated, or for administrative and/or other safety reasons. Specific details regarding discontinuation or withdrawal are provided in Section [7.1.3](#) – Other Procedures.

A subject must be discontinued from the trial, with no further data reporting, for the following reasons:

- The subject withdraws consent
- Subject death
- The subject is lost to follow-up

A subject must be discontinued from study treatment, but will continue to be followed, for the following reasons:

- Confirmed radiographic disease progression
 - *Note:* For unconfirmed radiographic disease progression, please see RECIST 1.1 criteria
 - *Note:* A subject may continue on treatment with confirmed radiographic progression if clinically stable or clinically improved, please see RECIST 1.1 criteria, after discussion with the sponsor.
- Unacceptable adverse experiences as described in Section [7.2](#)
- Investigator's decision to withdraw the subject
- The subject has a confirmed positive serum pregnancy test
- Noncompliance with trial treatment or procedure requirements
- Completed 12 months of treatment with study drug(s)
 - *Note: 12 months of study medication is calculated from the date of first dose. Subjects who stop treatment after 12 months may be eligible for additional study treatment if they progress after stopping study treatment provided they meet the requirements detailed in Section [7.1.4.2.1](#).*
- Administrative reasons
- Sponsor decision to terminate the trial

- Subject is determined to have met one or more of the exclusion criteria for study participation at study entry and continuing investigational therapy might constitute a safety risk

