7.2.3.2 Events of Clinical Interest

Selected non-serious and serious adverse events are also known as Events of Clinical Interest (ECI) and must be recorded as such on the Adverse Event case report forms/worksheets and reported within 24 hours to the Sponsor and within 2 working days to inVentiv Health Clinical Pharmacovigilance (Attn: iHC SAE Reporting; [contact] or email: [contact]).

Events of clinical interest for this trial include:

1. Pneumonitis - Pneumonitis has been reported in association with use of anti-PD-L1/anti-PD-1 antibodies [36]. Initial work-up should include a high-resolution CT scan, ruling out infection, and pulse oximetry. Pulmonary consultation is recommended.
2. Hypersensitivity Reactions - Hypersensitivity reactions as well as infusion-related reactions have been reported with anti-PD-L1 and anti-PD-1 therapy [36]. As with the administration of any foreign protein and/or other biologic agents, reactions following the infusion of mAbs can be caused by various mechanisms, including

acute anaphylactic (IgE-mediated) and anaphylactoid reactions against the mAb, and serum sickness. Acute allergic reactions may occur, may be severe, and may result in death. Acute allergic reactions may include hypotension, dyspnea, cyanosis, respiratory failure, urticaria, pruritis, angioedema, hypotonia, arthralgia, bronchospasm, wheeze, cough, dizziness, fatigue, headache, hypertension, myalgia, vomiting and unresponsiveness.

- Subjects with Grade 1 and 2 hypersensitivity (including anaphylactic reaction) and infusion-related reactions should be treated according to standard medical practices. If a subject experiences a grade 3 or 4 infusion reaction, the infusion will be discontinued immediately, and no subsequent infusions may be given.
- A grade 3 or 4 infusion reaction will require immediate treatment, including the use of epinephrine, bronchodilators, and/or glucocorticoids for symptomatic bronchospasm; IV fluids and/or pressors for hypotension; and immediate and permanent discontinuation of study drug(s) with appropriate supportive care.

3. Hepatic Function Abnormalities (Hepatotoxicity) - Increased transaminases have been reported during treatment with anti-PD-L1 [\[36\]](#).

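### After a Grade 3 infusion reaction, Table 5 allows further treatment following sponsor discussion, while Section 7.2.3.2 forbids any further infusion; the conflict holds at least for MEDI4736

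*Combined protocol and SAP*

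**What the plan says.** Section 5.6.4 introduces Table 5 as the guide for managing infusion reactions and gives it a general scope: "With any infusional therapy there is the possibility of an infusion reaction". Item 5 of its row for Grades 3 and 4 separates the two grades. Grade 4 ends trial treatment for good. For the lower grade it says "Subjects with Grade 3 reactions may continue after discussion with the sponsor".

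Section 7.2.3.2, item 2, covers hypersensitivity and infusion-related reactions as events of clinical interest. Its first bullet says "If a subject experiences a grade 3 or 4 infusion reaction, the infusion will be discontinued immediately, and no subsequent infusions may be given". Its second bullet, for the same two grades, requires "immediate and permanent discontinuation of study drug(s) with appropriate supportive care". Neither bullet mentions an exception by agreement with the sponsor.

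Section 5.8 opens a mandatory list with "A subject must be discontinued from study treatment, but will continue to be followed, for the following reasons". The list includes unacceptable adverse experiences and points to Section 7.2 for their description.

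**The concern.** The two sections address the same event at the same grade. One grants a permission that the other withholds. A site managing a reaction would naturally open Table 5, while a site completing the event-of-interest report would open Section 7.2.3.2, and the two could act differently on identical cases.

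What is at stake is re-exposure after a severe reaction. Table 5 describes Grade 3 as a reaction that is prolonged, that recurs after first improving, or that calls for hospital care because of sequelae such as renal impairment. Section 7.2.3.2 warns that acute allergic reactions can be fatal. Section 8.2 says that no external data safety monitoring committee will be set up and that an internal team will review safety periodically. The written stopping rule therefore carries more of the load.

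**Working it through.** No arithmetic applies; the check is a comparison of the current text. Nothing here depends on redacted wording or on the summary of changes.

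1. **Same event and grade.** Both texts concern an infusion reaction of Grade 3. They agree at Grade 4, where both stop treatment permanently. They part only at Grade 3.

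2. **What each text allows at Grade 3.** Table 5, item 5: the subject may go on once the sponsor has been consulted. Section 7.2.3.2, item 2: no later infusion, and permanent discontinuation.

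3. **Can a site satisfy both?** Yes, by stopping, since Table 5 permits continuation without requiring it. A site that uses the permission, even with the sponsor's agreement, breaches Section 7.2.3.2. The conflict is therefore between a permission and a prohibition.

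4. **Which drug?** Table 5 reaches any infused therapy, so it covers both products. Item 2 of Section 7.2.3.2 opens with reactions reported for anti-PD-L1 and anti-PD-1 antibodies, which suggests MEDI4736, but its second bullet refers to study drugs in a form that may be singular or plural. The overlap is certain for MEDI4736. It extends to ADXS11-001 only if that phrase is taken literally.

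5. **Is precedence stated?** Neither Table 5 nor Section 7.2.3.2 refers to the other on this point. Section 5.8 makes stopping compulsory for unacceptable experiences described in Section 7.2. That favours the stricter text, but it does not say that it overrides Table 5.

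6. **Does the dose-limiting toxicity list settle it?** No. Section 5.2.1.2 exempts a Grade 3 infusion-related reaction that resolves within 6 hours, but this governs what counts as a dose-limiting toxicity in Part A, not whether the subject is dosed again. Item 10 of the same list withholds further doses after a related allergic reaction of Grade 2 or higher not due to antibiotic. That leans toward the stricter rule in Part A, but covers only allergic reactions.

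7. **Overlap with Table 3.** After a first Grade 3 or 4 episode of cytokine-release symptoms on ADXS11-001, Table 3 lengthens the infusion and suggests more prophylaxis; it does not stop treatment. Its examples include chills, rigors, hypotension and fever. Section 5.6.4 lists rigors or chills, hypotension and drug fever among the signs of an infusion reaction. A stop rule for infusion reactions that is not limited by drug would therefore collide with Table 3.

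**The case against.** The strongest reply is that the risk is already contained. Stopping breaches neither text, Section 5.8 is mandatory where Table 5 is a guideline, continuation under Table 5 needs a discussion with the sponsor in each case, and these reactions are reportable to the sponsor within 24 hours as events of clinical interest. All of that is correct and makes unreviewed re-exposure less likely. None of it tells the site or the sponsor which of the two rules decides the case once they are talking.

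A second reply is that Section 7.2.3.2 concerns the antibody only. That narrows the point without removing it, because Table 5 covers MEDI4736 as well.

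A reader might go further and infer a third, separate outcome from Table 4. Its Grade 3 cell under All Other Events has a clause that begins "For AEs that downgrade to" Grade 2 or lower within 7 days and ends "or baseline within 14 days, resume MEDI4736/Combination administration at next scheduled dose. Otherwise, discontinue MEDI4736/Combination". It requires no sponsor discussion and does not exclude infusion reactions. The documents do not support treating this as a third competing rule. The table is titled "Dose Modification Guidelines for Immune-related Adverse Events - MEDI4736 Monotherapy and Combination Arms" and never names infusion reactions, and Section 5.6.4 sends the reader to Table 5 for them. If a reaction were classed as immune-related, the Grade 3 entry of Table 4 for other immune-related events would require discontinuation, in line with Section 7.2.3.2. What remains is a minor ambiguity worth one clarifying sentence.

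**Conclusion.** The contradiction between Table 5, item 5, and Section 7.2.3.2, item 2, is real and needs correcting. It applies to Grade 3 reactions, at least for MEDI4736, with no stated precedence and a lean toward the stricter text through Section 5.8. Its effect is on subject safety and protocol compliance.

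No count of affected subjects can be given. The nearest figure is in Section 5.6.1, which puts Grade 3 rigors and hypotension with ADXS11-001 below 5%, without a denominator. That concerns cytokine-release symptoms with the other product, so it cannot serve as a rate for MEDI4736 reactions. No endpoint, sample size or statistical figure changes.

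A reader might also infer that every infusion of either drug should stop after any Grade 3 reaction. The documents do not support that, because Table 3 deliberately keeps subjects on ADXS11-001 after a first severe cytokine-release episode with overlapping signs. The conclusion rests on reading Table 5 as covering MEDI4736, which its general scope makes plain.

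**What to change.** - Change the last sentence of Table 5, item 5, so that a Grade 3 or 4 infusion reaction to MEDI4736 means no further MEDI4736, matching Section 7.2.3.2. If the sponsor's medical lead prefers to keep the exception, write it into Section 7.2.3.2 in the same words as Table 5.
- State in both places whether a combination subject who stops MEDI4736 for this reason also stops ADXS11-001.
- State in both places that ADXS11-001 cytokine-release symptoms (rigors, chills, hypotension, fever) are managed under Table 3 and fall outside this stop rule.
- As a minor clarification, add to the All Other Events column of Table 4 that infusion reactions follow Table 5.

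The cost is a wording amendment and a letter to sites. Under the stricter rule there may be a few more MEDI4736 discontinuations. No extra subjects or procedures are needed.
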